2.1 General Considerations

The objective of this double-blind Phase II study is to evaluate the efficacy and safety of AQX-1125 (200 mg) in male subjects with chronic prostatitis/chronic pelvic pain Syndrome (CP/CPPS). This study uses a randomized (1:1, AQX-1125: Placebo), double-blind, placebo-controlled, parallel group design. Randomization will be conducted at Baseline (Visit 2), after verifying that the subject meets all inclusion criteria and has none of the exclusion criteria. Two tablets of AQX-1125 or placebo will be administered orally once daily for 12 weeks. The study will consist of a screening period of up to 3-weeks a 12-week treatment period followed by a 4-week off drug Safety Follow-up period, and an Ophthalmic Safety Follow-up Visit 6-months post last dose, for a total study duration of about 41 weeks. There will also be a follow-up telephone call 3 months after the last dose.

All subjects screened into the study will be assigned a subject identifier number during screening that will be used on all subject documentation. The subject identifier number will contain the site number and the subject number assigned in numerical order at the screening visit. Subject numbers will be assigned in ascending order at each site starting with 01. All data will be listed in subject data listings sorted by site and subject number unless otherwise noted. Data tabulations will be prepared as described in the sections below.

All statistical analyses will be performed using SAS Version 9.4 or higher. The following summary statistics will be reported for continuous data: number of subjects, mean, median, standard deviation, quartiles, minimum, and maximum. Confidence intervals (CIs) will be provided where appropriate. For categorical data, the number and percentage of subjects within each treatment group will be reported.

For weekly scores that are based on daily subject assessments, a subject's score for a week will be the average (mean) of the daily scores across that week. Baseline lab test results or vital sign results will be the last non-missing value before dosing. Change from baseline will be defined as the post-baseline visit value minus the baseline value unless otherwise specified. Assessments performed at the Early Termination visit will be summarized descriptively.

2.2 Subject Population

2.2.1 Sample Size Justification

Sample size was calculated using the 2-sample means statement in the POWER procedure in SAS. A sample size of 45 subjects per treatment group will provide 80% power to detect a 1.2-point difference in the change from Baseline pain score

between AQX-1125 and placebo assuming a between-subject standard deviation of 2.0 and a 2-sided 5% significance level.

Assuming a 10% rate of discontinuation from study drug, the total number of subjects to be randomized is approximately 100. Subjects who discontinue will be included in the primary analysis, resulting in a slight decrease in power if the discontinuing subjects in the placebo group have no additional change after discontinuation of study drug while the discontinuing subjects in the AQX-1125 group have a loss of efficacy after discontinuing study drug.

2.2.2 Study Assessment Time Points

All enrolled subjects will record the maximum and average daily pelvic pain in the eDiary from Screening Visit 1 to Week 16, as well as analgesic medication taken each day. Subjects will record 24-hour voiding frequency prior to scheduled visits at baseline, Week 6, Week 12 and Week 16. Visits are scheduled at the following timepoints:

- Visit 1/Screening
- Visit 1a/ Baseline ophthalmic assessments (at any time before Visit 2)
- Visit 2/Baseline (Week 1)
- Visit 3 (Week 6)
- Visit 4 (Week 12)
- Early Termination: Subjects who withdraw from the study during the treatment period should complete an Early Termination Visit. Subjects who discontinue the double-blind treatment for any reason will be encouraged to continue with all subsequent study-related visits and a visit at Week 12 to assess efficacy endpoints.
- Off Treatment (Week 16) 4-week off drug Safety Follow-up period
- Ophthalmic Safety Follow-up Visit 6-months post last dose: Ophthalmic assessments and AE collection (ophthalmic related AEs only)
- Follow-up telephone call 3 months after the last dose: AE collection (ophthalmic related AEs only)
- Unscheduled Visits: Unscheduled visits may occur when subject needs to make a visit in between the scheduled visit dates due to an AE, difficulty complying with the study protocol requirements, or a significant change in their disease state. Unscheduled visits may be conducted at any time during the study and should include the same assessments as Week 16.

| Event | Screening Period ^a | | Baseline | Treatment Period | | ET ^j | Safety Follow-up | | |
|--|-------------------------------|----------------------------|----------|------------------|----------------|-----------------|------------------|-----------------|-----------------------------|
| | Visit 1 | Baseline Ophthal. Visit 1a | | Visit 2 | Visit 3 | | Visit 4 | Off-Treatment | Telephone call ^k |
| Week | | | 1 | 6 | 12 | NA | 16 | 25 | 38 |
| Day (± window) | -14 (±7) | Before Visit 2 | 1 | 42 (±3) | 84 (±3) | NA | 112 (±3) | 175 (±7) | 266 (±7) |
| 24-hour voiding frequency ^h | | | ✓ | ✓ | ✓ | ✓ | ✓ | | |
| AE collection | ✓ | | ✓ | ✓ | ✓ | ✓ | ✓ | ✓ ^l | ✓ ^l |
| Concomitant medications | ✓ | | ✓ | ✓ | ✓ | ✓ | ✓ | | |
| Study drug dispensing ⁱ | | | ✓ | ✓ | | | | | |
| Study drug compliance check | | | | ✓ | ✓ | ✓ | | | |
| Study drug accountability | | | | ✓ | ✓ | ✓ | | | |
| eDiary Issue/Train/Review/Collect | I/T | | R | R | R | R | R/C | | |

Abbreviations: AE=adverse event; BCVA=best corrected visual acuity; BP=blood pressure; C=collect; ECG=electrocardiogram; eDiary=electronic diary; ET=Early Termination; GRA=Global Response Assessment; HR=heart rate; I=issue; IIEF =International Index of Erectile Function; IOP=intraocular pressure; LOCS= Lens Opacity Classification System; LogMAR=Logarithm of the Minimum Angle of Resolution; NA=not applicable; NIH-CPSI=National Institute of Health Chronic Prostatitis Syndrome Index; NRS=Numerical Rating Scale; PCS=Pain Catastrophizing Scale; PGI-C=Patient's Global Impression of Change scale; PGI-S=Patient's Global Impression of Severity scale; PHQ-9=Patient Health Questionnaire; R=review; T=train; UPOINT=Urinary, Psychosocial, Organ Specific, Infection, Neurologic/Systemic, Tenderness of Skeletal Muscles.

^a Minimum screening period is 7 days, which includes the baseline ophthalmic assessment at Visit 1a.

^b Demographics include age, birth year, sex, race and ethnicity.

^c Questionnaires must be completed prior to other assessments.

^d Paper-based 11-point NRS will be administered in-clinic during the study visit to assess the average and maximum daily pelvic pain.

^e Ophthalmic assessments include BCVA using the LogMAR chart (i.e. after manifest refraction), IOP (preferably measured by Goldmann tonometry, before and after dilation with mydriatic agent) corneal staining, slit lamp examination, and lenticular opacification using LOCS III. Baseline ophthalmology assessment can be completed as a separate visit any time during the screening period (any time before Visit 2). Background incidence of cataracts in subjects noted prior to dosing should be recorded as medical history. Ophthalmic assessments at all post-Baseline Visits should occur within the specified Visit windows.

^f Subjects will be resting supine for at least 5 minutes before the ECG recording.

^g Clinical chemistry does not need to be fasting.

^h Voiding frequency will be measured over a 24-hour period, within a 3-day (72 hours) window before the scheduled visits.

ⁱ The first dose of study drug at Baseline (Visit 2) will be administered in the clinic. At subsequent Visits, subjects are to refrain from taking study drug at home on the morning of the clinic visit day and should be dosed in the clinic.

^j If a subject withdraws from the study, all assessments for the ET Visit should be conducted.

^k Subjects who withdraw from the study anytime during the study will have a follow-up period of 6 months, consisting of an Off-Treatment Safety Follow-up Visit (4 weeks post last dose), telephone call follow-up (3 months post last dose) and ophthalmic assessment (6 months post last dose).

- ^l Subjects will be asked for updates on new and ongoing (after the 28 days follow-up) ocular AEs only.
- ^m Repeat at Off-Treatment Safety Follow-up is only needed if there are outstanding safety concerns from Week 12.
- ^N Score will not be recorded in the database, assessment will be performed for patient safety/monitoring purposes only clinically significant findings will be reported as adverse events.

NOTE: Unscheduled visits may be conducted at any time during the study and may include the same assessments as Week 12.

2.2.4 Randomization/Unblinding

2.2.4.1 Randomization Methodology

Approximately 100 male subjects with diagnosed CP/CPPS will be randomized to either AQX 1125 (200 mg) or placebo in a 1:1 ratio.

A central, permuted block randomization scheme will be used with a selected blocking factor (block size) determined based on the proposed allocation ratio and number of subjects. The block size will be specified in the randomization plan.

An Interactive Web Response System (IWRS) will be used for the randomization to either AQX-1125 (200 mg) or placebo and subsequent wallet assignments. Study staff will log in to the IWRS using unique credentials and input subject-specific screening and baseline information. In accordance with the randomization schedule, the IWRS will assign the randomization number and unique wallet numbers to the subject. Each subject must be given only the wallets assigned by IWRS. The study staff will document the wallet number in the Study Drug Accountability electronic Case Report Form (eCRF). Subjects are to be randomized in the order in which they qualify from the screening phase for inclusion in the study. The randomization plan will be executed in accordance with CTDS' SOP DM016: Generation of Randomization Schemes/Unblinding.

2.2.4.2 Unblinding

The investigators, study personnel, subjects, medical monitor, and clinical monitor will remain blinded throughout the study, unless safety concerns necessitate unblinding.

If a medical emergency occurs and a decision regarding the subject's clinical treatment requires knowledge of the treatment assignment, the study blind may be broken for the specific subject. Unless the medical emergency is deemed to be life-threatening, the medical monitor must first be consulted before unblinding. The Investigator would then utilize the IWRS for unblinding and the unblinding procedure will be provided in the eCRF Completion Guidelines. The date, time, and reason for unblinding must be documented in the source documents and on the applicable unblinding form in the IWRS. Investigators should note that the occurrence of a SAE should not routinely trigger immediate unblinding. If the medical monitor was not notified prior to breaking the

blind, the investigator must notify the medical monitor of any and all blinks broken within 24 hours of each occurrence.

2.2.5 Study Populations for Analysis

The following are the analysis populations to be used:

2.2.5.1 Intent to Treat (ITT) Population

The ITT Population will include all randomized subjects. In the event of study drug administration error, analyses on the ITT Population will be performed according to the treatment which the subject was randomized to receive.

2.2.5.2 Safety Population

The Safety Population will include all subjects who received any amount of study drug. In the event of study drug administration error, analyses on the Safety Population will be performed according to the treatment the subject actually received.

2.2.5.3 Per-Protocol (PP) Population

The PP Population will include all ITT subjects who do not have any major protocol deviations that possibly affect interpretation of the primary efficacy endpoint and have non-missing Baseline and Week 12 assessments of maximum daily pelvic pain (i.e. the primary efficacy assessment). Determination of which subjects to be included in the PP population will be performed by a blinded review committee prior to database lock. In the event of study drug administration error, the subject will be omitted from the PP population.

2.2.6 Baseline Characteristics/Medical History

Demographics – age (years), race, ethnicity and baseline height, weight BMI and baseline maximum daily pelvic pain will be summarized by treatment group and overall for the ITT, Safety, and PP Populations.

Medical History will be coded using the MedDRA dictionary terms and will be summarized by SOC and PT by treatment group and overall for the ITT Population.

2.2.7 Subject Disposition

All subjects enrolled into the study that are issued a subject number will be accounted for in Subject Disposition. Data will be tabulated by treatment group and overall and the numbers and percentages of subjects in each treatment group

who are enrolled, randomized and treated, who comprise each of the analysis populations, who complete the study or discontinue from treatment or discontinue from the study prematurely along with the reason for discontinuation will be presented. The number of subjects who were seen at each specified study visit will also be tabulated by treatment group and by site.

Reasons for any early withdrawals and the last date of dosing completed prior to discontinuation will be provided in a listing.

2.2.8 Protocol Deviations

Protocol deviations (major and minor) will be defined prospectively prior to database lock by a review committee who is blinded to treatment assignment. Deviations will not be entered by the clinical sites into the EDC database. Instead, they will be tracked separately by the ProTrial's clinical personnel. This process will be defined in detail in the ProTrial's separate Protocol Deviation Plan document. Major protocol deviations as well as those deviations that could possibly affect the interpretation of the primary endpoint (subset of major deviations) will be tabulated by treatment group and overall. All deviations will be presented in listings. All deviations will be classified and excluded from the PP analysis.

2.2.9 Dose Regimen

Two AQX-1125 100 mg tablets will be administered orally once daily, around the same time of day, with food or eat a light meal no more than 4 hours prior to consumption, for 12 weeks. Matching placebo is identical in appearance to the test product and contains no active ingredient and will be administered the same as AQX-1125. Tabulations of exposure to study medication are described in Section 2.2.15.1, Extent of Exposure. Details of study medication use will be provided in a subject data listing.

2.2.10 Methods for Handling Missing Data

2.2.10.1 Missing Daily Data in the Weekly Scores

For endpoints which are the average of a daily score across a week (e.g., maximum daily pain and average daily pain), if the subject has 4 or more non-missing values in that week, the weekly mean score will be calculated as the average of the non-missing values, otherwise the weekly mean score will be set to missing for that week.

2.2.10.2 Imputation Methods

The primary endpoint analysis method is a mixed model for repeated measures (MMRM) ANCOVA. This is an observed case approach to missing data and assumes the missing data is missing at random (MAR).

Sensitivity analyses for the primary efficacy analysis will include imputing the missing data using two multiple imputation (MI) methods (described below). Any sensitivity analyses performed will be considered supportive analysis.

- Multiple Imputation Assuming Missing at Random: Missing post-baseline weekly maximum daily pelvic pain (mean) change from baseline scores at Weeks 6 and 12 will be imputed via MI assuming (MAR). SAS Proc MI using the linear regression method will be the method for the imputation if the missing data pattern follows a monotonic pattern. If the data does not follow a monotonic pattern a sequential approach to imputing the variables to produce a monotone missing data pattern as described in Alut (2012) will be applied.

A default random number generator of 345353 will be used and 100 imputed datasets will be created. Each of the imputed datasets will be analyzed via the same model as the primary efficacy endpoint analysis (See Section 2.2.13.1). The range of the imputed pain values will be set between 0 and 10 via the SAS Proc MI Maximum and Minimum options. The results across the multiple imputed data sets will be combined using SAS Proc MIANALYZE.

The following are the set of variables to be used in the MI model:

- treatment group (placebo/AQX-1125)
- age group (<65, 65-<75, ≥75 years)
- race (White/Non-White)
- baseline daily pelvic pain score
- experienced a severe AE (yes/no) (CTCAE grade 3-5, severe, life-threatening or death)
- duration of exposure [last day-first day] +1

For the ‘experienced a severe AE’ imputation variable, if a subject experiences a severe AE from baseline to Week 6 the value will be ‘yes’ for the imputation of the Week 6 time-point, ‘no’ otherwise. Similarly, if a subject experiences a severe AE from Baseline to Week 12 the value will be ‘yes’ for the imputation of the Week 12 time-point, ‘no’ otherwise.

Note: if the MI model does not converge or produce estimates (i.e., due to over-specification) the set of imputation variables may be modified.

- Multiple Imputation Assuming Missing Not at Random: For this imputation the missing weekly maximum daily pelvic pain (mean) change from baseline scores will be imputed at Weeks 6 and 12 assuming the data follow a Missing Not at Random (MNAR) pattern. The imputation of weekly mean change from baseline pain scores in the AQX-1125 treatment group will be based on the distribution in the placebo group. This method assumes that the trajectory of withdrawals from the AQX-1125 treatment arm follows the distribution of the placebo subjects. Placebo-based imputation will be implemented by the sequential modelling approach via PROC MI (O'Kelly & Ratitch., 2014). Missing change from baseline endpoint values will be imputed using the distribution of the non-missing placebo group values. SAS Proc MI using the linear regression method will be the method for the imputation if the missing data pattern follows a monotonic pattern. If the data does not follow a monotonic pattern a sequential approach to imputing the variables to produce a monotone missing data pattern as described in Alut (2012) will be applied.

A default random number generator of 345354 will be used and 100 imputed datasets will be created. Each of the imputed datasets will be analyzed via the same model as the primary efficacy endpoint analysis (See Section 2.2.13.1). The range of the imputed pain values will be set between 0 and 10 via the SAS Proc MI Maximum and Minimum options. The results across the multiple imputed data sets will be combined using SAS Proc MIANALYZE.

The set of variables for the MI model is the same set as defined for the MAR MI imputation.

Note: if the MI model does not converge or produce estimates (i.e., due to over-specification) the set of imputation variables may be modified.

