At Baseline (Visit 2), all subjects will return to the clinic for review of eligibility and to complete the efficacy questionnaires and assessments to establish Baseline values. Average daily pelvic pain scores recorded in the eDiary within the 7 days prior to Baseline (Visit 2) will be part of the study entry criteria. If all entry criteria are met, the subject will be randomized (1:1) to receive a single daily oral dose of 2 tablets for 12 weeks as follows:

- AQX-1125 200 mg dose group: 2 AQX-1125 100 mg tablets; or,
- Placebo group: 2 placebo tablets

All enrolled subjects will record the following in the eDiary (from Screening Visit 1 to Week 16 [Off-Treatment Safety Follow-up Visit]):

- Maximum daily pelvic pain: subjects will assess their maximum pelvic pain for that day on a scale of 0 to 10, with 0 indicating 'no pelvic pain' and 10 indicating 'pelvic pain as bad as you can imagine'
- Average daily pelvic pain. Subjects will assess their average pelvic pain for that day on a scale of 0 to 10, with 0 indicating 'no pelvic pain' and 10 indicating 'pelvic pain as bad as you can imagine'
- Analgesic medication taken each day

- 24-hour voiding frequency: voiding frequency will be measured over a 24-hour period, within a 3-day (72-hours) window before the next scheduled visit (Visit 2, 3, 4 and Off-Treatment Safety Follow-up Visit)

At Week 6 (Visit 3), and Week 12 (Visit 4), and Week 16 (Off-Treatment Safety Follow-up Visit) during the clinic visit, subjects will complete NIH-CPSI, paper-based 11-point NRS (average and maximum pelvic pain experienced over the last 24 hours), GRA, PHQ-9, PGI-C, IIEF, PGI-S, have vital signs assessed and return unused study drug (Week 6 and 12). Any adverse events (AEs) are to be recorded.

Subject compliance with the eDiary will be monitored by trained study site personnel at each study visit.

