 - Decrease in maximum daily pelvic pain (mean) from Baseline to Week 12 using a standardized 11-point NRS with no change in the amount or strength of concomitant analgesic medications (as defined in Section 2.2.14).
 - Decrease in maximum daily pelvic pain from Baseline to Week 12 using a standardized 11-point NRS with a decrease in the amount or strength of concomitant analgesic medications (as defined in Section 2.2.14).
- (2) A $\geq 30\%$ and $\geq 50\%$ improvement (decrease) in maximum daily pelvic pain (mean) (using the 11-point NRS recorded by eDiary and the NIH-CPSI pain subscale), at Weeks 6 (Visit 3) and 12 (Visit 4).

For the Discontinuation of study medication due to treatment failure endpoint, only summary statistics will be provided for the percent meeting treatment failure criteria and the time to event (no inferential analyses will be performed). Time to discontinuation of study medication due to treatment failure will be summarized and presented graphically using Kaplan-Meier methods (i.e., SAS PROC LIFETEST stratifying on treatment group).

The frequency distribution of the 5-category IIEF-EF score will be presented by treatment group for Week 12 as well as a shift table from Baseline. The 5 categories are no erectile dysfunction (score: 26-30), mild erectile dysfunction (score: 22-25), mild to moderate erectile dysfunction (score: 17-21), moderate erectile dysfunction (score: 11-16) and severe erectile dysfunction (score: 1-10). Responses to all items must be completed to calculate an IIEF-EF score. Any response with missing values will be excluded from the analyses. Treatment group difference

with corresponding 95% CIs in the 5-category IIEF-EF will be assessed by a Cochran-Mantel-Haenszel (CMH) test using row mean scores controlling for Baseline IIEF-EF score.

Data from both treatment arms will be used to calculate a meaningful change threshold (MCT), which reports a change in the primary endpoint (change in maximum daily pelvic pain) by anchoring to other outcomes (including PGI-S and/or PGI-C) to determine a change in maximum pelvic pain that provides a meaningful benefit to patients. The determination of the MCT will be made outside of the methods documented in this SAP prior to database lock. Once the MCT is determined, the proportion of subjects who have an improvement of at least the MCT will be summarized by treatment group and compared using a chi-square test as an exploratory analysis.

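### Both multiple-imputation sensitivity analyses impute change from baseline but limit it to 0–10, the raw pain range, so no imputed visit can show improvement

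*SAP*

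**What the plan says.** SAP 2.2.10.2 describes two imputation analyses that support the primary MMRM.

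- **MAR version.** The imputed variable is the weekly mean of maximum daily pain, expressed as change: "change from baseline scores at Weeks 6 and 12 will be imputed via MI assuming (MAR").
- **Placebo-based (MNAR) version.** The variable is the same: "Missing change from baseline endpoint values will be imputed using the distribution of the non-missing placebo group values".
- **Range, stated in both bullets.** "The range of the imputed pain values will be set between 0 and 10 via the SAS Proc MI Maximum and Minimum options".

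Three other places in the SAP fix the scale and the sign. Section 2.1 states: "Change from baseline will be defined as the post-baseline visit value minus the baseline value unless otherwise specified". Section 2.2.13.3 treats a fall in pain as benefit: "improvement (decrease) in maximum daily pelvic pain (mean"). The synopsis gives the range of the raw diary item, on which subjects rate "their maximum pelvic pain for that day on a scale of 0 to 10".

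Each completed dataset then goes through the model in SAP 2.2.13.1, whose dependent variable is change from baseline; the sample code in Appendix B does the same. Section 2.2.10.2 also sets the status of these analyses: "Any sensitivity analyses performed will be considered supportive analysis".

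**The concern.** The named variable and the stated range do not belong together. A change score that is negative for improvement cannot sensibly have a minimum of 0. The upper limit does not fit either: from a baseline of 6.5, any change above +3.5 implies a pain score above 10.

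Programmed literally, neither analysis represents its own assumption. The MAR version does not draw from the distribution that MAR implies, and the placebo-based version does not draw from the placebo distribution. These are the only two analyses that test how the primary result depends on missing data by imputing it. If either disagreed with the primary MMRM, a reader could not tell sensitivity to missing data from an artefact of the limits.

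**Working it through.** **The plan's own figures.** SAP 2.2.1 gives a difference of 1.2, SD 2.0, two-sided 5% and 45 per arm for 80% power. A two-sample t-test with these inputs has 79.5% power at 44 per arm and 80.4% at 45, and 90 / 0.90 = 100. The sample size reproduces, and this point does not touch it.

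**Inputs.** From the plan: SD 2.0, difference −1.2, 10% discontinuation of study drug. Assumed, because the documents do not give them: placebo mean change −0.5 to −2.0 (active 1.2 lower), residual SD 1.6 as an alternative to 2.0, and the missingness in each arm.

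**Step 1: what the limits remove.** The chance that an imputed visit shows improvement is exactly 0, with no assumption needed. The share that should show improvement is Φ(−μ/σ). The mean of a normal variable restricted to [0, 10] is μ + σ·[φ(a) − φ(b)] / [Φ(b) − Φ(a)], with a = (0 − μ)/σ and b = (10 − μ)/σ. At σ = 2.0:

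| Placebo / active mean | Share below 0, placebo / active | Imputed mean, placebo / active |
|---|---|---|
| −0.5 / −1.7 | 60% / 80% | +1.43 / +1.11 |
| −1.0 / −2.2 | 69% / 86% | +1.28 / +1.01 |
| −1.5 / −2.7 | 77% / 91% | +1.16 / +0.92 |
| −2.0 / −3.2 | 84% / 95% | +1.05 / +0.85 |

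At σ = 1.6 the imputed means are +0.77 to +1.11 (placebo) and +0.60 to +0.82 (active).

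**Step 2: arm means.** With a fraction f missing, arm mean = (1 − f)·observed mean + f·imputed mean. Take placebo −1.5, σ = 2.0 and 10% missing in each arm, under MAR:

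- Placebo: 0.9 × (−1.5) + 0.1 × 1.16 = −1.23, instead of −1.5.
- Active: 0.9 × (−2.7) + 0.1 × 0.92 = −2.34, instead of −2.7.
- Difference: about −1.10, instead of −1.20.

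**Step 3: treatment difference.** In the placebo-based version the missing active values use the placebo imputed mean. Ranges below cover placebo means −0.5 to −2.0 and both SDs. The unbounded MAR difference is −1.20 throughout.

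| Missing, active / placebo | MAR, bounded | Placebo-based, bounded | Placebo-based, unbounded |
|---|---|---|---|
| 5% / 5% | about −1.15 | −1.14 | −1.14 |
| 10% / 10% | about −1.10 | −1.08 | −1.08 |
| 15% / 5% | −0.75 to −0.90 | −0.71 to −0.86 | −1.02 |
| 5% / 15% | −1.32 to −1.46 | −1.30 to −1.45 | −1.14 |

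With equal missingness the placebo-based difference is (1 − f) × (−1.2) whatever value is imputed, so the limits cancel there, although both arm means still shift.

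**Step 4: no drug effect.** With both means at −1.5 and σ = 2.0, each missing value is shifted by 1.16 − (−1.5) = 2.66. At 16% missing in one arm and 4% in the other, the spurious difference is (0.16 − 0.04) × 2.66 = 0.32, against the arm with more missing data.

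**Step 5: simulation.** This used 50 per arm, placebo mean −1.5, Weeks 6 and 12 correlated 0.6 (assumed), 20 imputations, Week 12 ANCOVA and 400 replicates (Monte Carlo error about 2 percentage points). MAR power, bounded against unbounded, was 75% v 83% at 10%/10%, 37% v 84% at 16% active/4% placebo, and 94% v 81% at the reverse. With no drug effect, 16%/4% in either direction gave a spurious difference of 0.31 in size and rejection of 10–12%, against 4–5% unbounded.

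**The case against.** The best reply is that the range sentence changes the noun. It limits *pain values*, and 0 to 10 is exactly the raw scale, so the author probably meant raw scores to be imputed and change derived afterwards. That may well be right. But the SAP nowhere gives that step, both bullets name change from baseline as the imputed variable, and the model they feed uses change. On this reading the range is right and the named variable is wrong; the text still needs correcting.

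Several limits on the size of the problem stand:

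- The bar on improvement applies to imputed visits only. A subject missing just Week 12 keeps an observed Week 6 improvement.
- The 10% in the plan is discontinuation of study drug, not missing Week 12 data, and discontinuers are encouraged to stay in follow-up (SAP synopsis and 2.2.2). Missing data may be below 10%.
- The unequal splits are illustrations; nothing in the plan predicts them. At milder splits the MAR difference is −1.08 to −1.11 (6% active/4% placebo) and −0.96 to −1.03 (12%/8%).
- The simulation simplifies the planned analysis: 20 imputations instead of 100, and a Week 12 ANCOVA instead of the MMRM. It indicates scale and direction only.

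None of these reconciles the imputed variable with its range.

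**Conclusion.** The concern holds and should be fixed. As written, the rule gives zero probability of an imputed improvement in both analyses; that follows from the text alone. The numerical effect rests on the assumed placebo mean, SD and missingness. With equal missingness it is small: about 0.1 point on the MAR difference at 10% per arm, and nothing on the placebo-based difference. With unequal missingness it can reach several tenths of a point in either direction, so it cannot be excused as conservative: more missing data on placebo inflates the apparent benefit.

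The scope is limited to these two supportive analyses. The observed-case primary MMRM, its p-value, the per-protocol repeat and the sample size are unaffected.

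**What to change.** In both bullets of SAP 2.2.10.2, state that the weekly mean maximum pain score at Weeks 6 and 12 is the imputed variable, with Minimum = 0 and Maximum = 10, and that change is then computed as imputed score minus baseline before the primary model is run.

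Imputing change and deleting the range would also remove the contradiction, but it is second best because it allows impossible scores. From a baseline of 6.5, with an active mean change of −2.7 and SD 2.0, about 2.9% of draws would imply pain below 0 (Φ[(−6.5 + 2.7)/2.0]).

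The cost is a few words in two bullets and one variable in the program. Data collection, patients, the primary analysis and the sample size do not change. It should be done before the unblinding that follows the Week 16 database freeze (SAP 2.2.12), so that the choice is not made after the results are seen.
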